Operation RANCH HAND personnel flew C-123 aircraft in RVN during 1962-1970. Data from hand-compiled lists obtained through the RANCH HAND Association (a reunion organization), Air Force personnel computer entries, historical records and actual C-123 flight orders, place the estimated study population at approximately 1200 individuals. Of those personnel confirmed by the USAF computer system, 25% are still on active duty, with the remainder being composed of retired or separated persons. An indepth search to identify all RANCH HAND participants is being conducted of all organizational records stored at the Military Records Division, National Personnel Records Center (NPRC), St. Louis, Missouri. Detailed advertisements in active/retired military trade journals, VA publications, and local newspapers may be pursued in the near future to insure maximal ascertainment/identification of the exposed group. Introductory letters will be sent to the last known address of all identified persons, and nonresponse will be pursued by cross-locator systems available within the government (e.g., Social Security Administration, VA, Internal Revenue Service). Significant efforts will be made to account for at least 99% of the total population (see Figure A-2, Section XII). Because of the limited number of estimated RANCH HAND personnel (1200), no subsampling of the exposed group is planned in any phase of the study. All members will be strongly encouraged to participate in all phases of the investigation.

(a) Known or Predicted Characteristics of the Exposed Group

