During the questionnaire and physical examination phases of this study, only one of the five randomly selected mortality study controls will be used for each RANCH HAND individual. If this control is unwilling to participate, another mortality study control will be used as indicated in Figures 2 and 5. These replacements will be carefully labelled for purposes of statistical comparison to the lost controls. Analysis without the replacements will also be accomplished, so that there will be no inferential loss from the use of replacements. A more detailed discussion of this replacement concept is found in section I below.

B. General Comments

Before proceeding to statistical details regarding this protocol, general areas of the overall design will be discussed.

(1) Adequacy of Sample Sizes

The size of R' is approximately 1000 individuals. It is clear that a lethal effect of herbicide which occurs in only 1 out of 2000 controls will be quite difficult to detect unless the herbicide effect is very strong. For example, at a rate of 1 in 2000, 0.5 affected controls are expected. If the basic rate is

doubled by herbicide to 2 per 2000, one affected RANCH HAND individual would be expected. At a rate of 1 per 2000 for controls and a rate of 2 per 2000 for RANCH HAND personnel, the probability of observing no affected individuals in both groups is

$$(1 - 1/2000)^{1000} (1 - 2/2000)^{1000} = .22$$

or, in other words, "there is a 22% chance" that no affected individuals will be found in this study. In a population of 100,000 exposed individuals, 100 cases would be expected, 50 of which would be due to herbicide. In short, since the size of the RANCH HAND group is fixed, this study has limited statistical power to define the relationship of herbicide to the rarer diseases.

(2) False Reporting/Misrepresentation

To understand the effect of misrepresentation on estimates of relative risk and the odds ratio, let S stand for presence of a symptom, and \bar{S} denote its absence. This false reporting may be represented as in Figure 7.

FIGURE 7

FALSE REPORTING/MISREPRESENTATION

		TRUE STATUS		
		S	\bar{S}	TOTAL
REPORTED STATUS	S	A	B	A + B
	\bar{S}	C	D	C + D
		A + C	B + D	

The proportion of correctly classified positives is defined by $A/(A+C)$ and is called the sensitivity of the classification scheme; the proportion of correctly classified negatives $D/(B+D)$ is called the specificity.

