Considering the basic groups R' and C' , individuals will be classified into three categories: alive, dead, unaccounted. If a large number of individuals of each group are unaccounted for, the study can obviously be severely biased. Thus, significant effort will be expended to reduce the unaccounted category as much as possible. At most 1 to 3 percent of both groups can be allowed to remain unaccounted, with a 1% rate being preferred. If for example, the mortality rate in C' is 0.10, then an unaccountability rate of 0.01 could alter the mortality rate by as much as 10%. Whatever the unaccountability rates, the pattern of unaccountability must also be compared between groups R' and C' . For example, the possibility of age differences or RVN tour length differences must be examined, particularly if the unaccountability rates are high. The following will discuss analysis of mortality under the assumption that low unaccountability rates have rendered the mortality analysis meaningful.

Two mortality analyses will be accomplished, one at the beginning of the study, using available mortality data on the basic cohorts C' and R' (1:5 ratio), and one several years later, using mortality data on R' and all controls used in the study (both C' and replacements) as it accumulates prospectively. The procedures described here and in Section E below can be used in both

analyses. Henceforth, within the protocol, the term "mortality data" does not distinguish between that data collected initially and that data collected in the future.

The mortality data will be analyzed using several different approaches. Crude age-specific death rates will first be calculated and tabulated. Age will be divided into k strata, and person-years will be observed for each strata as will be the number of deaths in each strata. In this manner a tabular display will be developed as shown in Table 7.

TABLE 7
STRATIFIED FORMAT OF AGE-SPECIFIC DEATH RATES

Age Group	Ranch Hand			Controls		
	Person Years	Deaths	Death Rate	Person Years	Deaths	Death Rate
1	P ₁₁	m ₁₁	r ₁₁	P ₂₁	m ₂₁	r ₂₁
2	P ₁₂	m ₁₂	r ₁₂	P ₂₂	m ₂₂	r ₂₂
3	P ₁₃	m ₁₃	r ₁₃	P ₂₃	m ₂₃	r ₂₃
⋮	⋮	⋮	⋮	⋮	⋮	⋮
⋮	⋮	⋮	⋮	⋮	⋮	⋮
⋮	⋮	⋮	⋮	⋮	⋮	⋮
k	P _{1k}	m _{1k}	r _{1k}	P _{2k}	m _{2k}	r _{2k}

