and α and β were obtained from the data. The function represents a fairly high rate disease in that at 40 years of age 7% of the group had the lesion and at 60 years of age 20% had the lesion. The coefficient γ , represents the exposure effect. Power calculations for $\gamma = \beta$ and $\gamma = .8\beta$ are shown in Table 13. This figure suggests that if, as a cell toxin, herbicide exposure accelerates cardiovascular disease, this study has a good chance of detecting that acceleration if the herbicide effect is comparable to the age effect. A slight beneficial effect of pairing is seen in this hypothetical example.

Cancer. A logistic risk function was fitted to breast cancer data presented by Breslow and Day (1975). The function fitted represents a low rate disease in that at 35 years of age only .000336 of the group had the lesion while at 70 years of age .00676 of the group will have the lesion. Using pairing to achieve a power of 0.80 in this setting, 1312 pairs would be needed, when the exposure effect is equal to the age effect. This exceeds the size of our RANCH HAND cohort, and reinforces the fact that herbicide exposure effects on rarer diseases will not have a high likelihood of being detected by this study, and again supports an attempt to examine as many pairs as possible.

TABLE 13

POWER CALCULATIONS AS A FUNCTION OF HERBICIDE EFFECT

ASSUMPTION: $\alpha = 0.05$

Number of Pairs	$\gamma = \beta$		$\gamma = .8\beta$	
	Power Neglecting Pairing	Power With Pairing	Power Neglecting Pairing	Power With Pairing
100	.93	.93	.64	.53 ($\alpha = .036$)
160	>.97	.98	.81	.82
200	>.99	>.995	.86	.87
250	>.99	>.995	.93	.95
300	>.99	>.995	.96	.97
350	>.99	>.995	.97	.98

G. Multivariate Analysis

Some questionnaire and physical examination data naturally fall into groups; for example, fertility/reproduction data, liver function tests, cardiovascular examination tests. In these cases, multivariate analysis may be in order. When the response variables are continuous, they will be analyzed by the well known multivariate extensions of the generalized linear model.

The general approach to multivariate analysis of polytomous data considers all classification factors and all variables as "factors" in a multi-way contingency table. Log-linear models as described above for polytomous data will be employed where appropriate.

H. Indices and Estimates of Exposure

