Study approaches generated by unprecedented occurrences of occupationally related medical complaints require novel approaches, and reorientation beyond standard methods. The success key to this study design is a series of effective, progressive, and helpful peer reviews (all of which have occurred to date and have been incorporated herein). Beyond even the immediacy of the current study is the growing problem of a myriad of occupationally-related exposures, both in the military and civilian sector, which will require similar epidemiological studies in the future in order to make some judgment as to whether or not an association is of causal significance.

B. Group Accountability Bias

(1) Problem

The numerous media presentations on "Herbicide Orange" issues have focused attention on the RANCH HAND group. Several attempts have been made to construct lists of former members of this group and thus the RANCH HAND population should be easier to locate and contact than the control population. This difference will be particularly evident with respect to reported mortality experience. The incentives for cooperation and study participation are likely to be greater in the exposed group than in the controls. Also, the close knit reunion association of former RANCH HAND personnel will lead to a more precise reporting of morbidity and mortality in that group. Such group identity tends to decrease the degree of unaccountability in the exposed group while its absence in the controls may lead to under ascertainment of mortality. This could then lead to the attribution of excess mortality in the exposed population.

(2) Corrective Measures

Unaccountability bias will be minimized by attempting to keep the percentages of unaccounted for study subjects below 1% in both exposed and control groups. The morbidity and mortality status of all individuals selected for the study will be strongly pursued utilizing a variety of techniques previously described.

C. "Risk Taking" Behavior Bias

(1) Problem

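### The mortality section tolerates up to 3% untraced men but works the bias only at 1%; at 3%, missed control deaths alone could produce a significant false excess

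*Protocol*

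**What the plan says.** Section VI.C (Analysis of Mortality Data) classifies men as alive, dead or unaccounted and sets the tolerance: "At most 1 to 3 percent of both groups can be allowed to remain unaccounted, with a 1% rate being preferred". For a control mortality of 0.10 it adds: "then an unaccountability rate of 0.01 could alter the mortality rate by as much as 10" percent. It also requires the pattern of unaccountability to be compared between groups, for example by age and tour length. It then presents the analyses on the assumption that unaccountability is low.

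Two other places give a tighter figure, both worded as aims. Section VIII.B (Group Accountability Bias) names as its corrective measure an attempt to "keep the percentages of unaccounted for study subjects below 1% in both exposed and control groups". Section V.B(1) (Exposed Group) promises efforts to "account for at least 99% of the total population", for the RANCH HAND population only.

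Section VIII.B also gives the expected direction. RANCH HAND men should be easier to locate, control deaths may be under-ascertained, and this could lead to excess mortality being attributed to the exposed group.

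**The concern.** The 3% figure appears only in section VI.C, and nothing in the protocol shows that it is tolerable. The wording also names two maxima, so a reader cannot tell whether 1% or 3% is the point beyond which the mortality analysis is considered unsafe.

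The bias is relative to the death rate, not to the size of the cohort. A few percent of men can be a large share of the deaths: at 10% mortality, 3% of the controls could be 30% of the control deaths. If those deaths are missed mainly in one group, the comparison shows an excess that comes from tracing. The protocol anticipates loss in that direction, and its results are expected to bear on compensation (section III), so a false excess would matter. Comparing the pattern of untraced men by age and tour shows who is missing. It does not bound how many of them are dead.

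**Working it through.** **Inputs**
- Control mortality m = 0.10: the illustration in section VI.C.
- Exposed group: "The size of R' is approximately 1000 individuals" (section VI.B(1)). Section V.B(1) gives about 1200, used as a sensitivity check.
- Five mortality controls per exposed man (section VI.C), so 5000 controls.
- Test level 0.05, as in the power tables of section VI.F. No level is stated for the mortality tests; two-sided is an assumption.
- No true effect: 100 deaths in 1000 exposed men, 500 true deaths in 5000 controls. RANCH HAND fully traced.

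**The plan's own figure.** Maximum relative change = u/m = 0.01/0.10 = 10%, as stated. At the plan's own upper tolerance, 0.03/0.10 = 30%.

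**Expected result when the lost controls are all dead.** The pooled two-proportion statistic is z = (p1 − p2) / √[p(1 − p)(1/n1 + 1/n2)]. Lost men are either counted as alive (denominator stays 5000) or excluded.

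- 1% lost (50 men), counted alive: 100/1000 v 450/5000. Pooled p = 550/6000 = 0.0917, SE = 0.0100, z = 0.010/0.0100 = 1.00, p = 0.32, ratio 0.10/0.09 = 1.11. Excluded: 450/4950, ratio 1.10, z = 0.91, p = 0.37.
- 3% lost (150 men), counted alive: 100/1000 v 350/5000. Pooled p = 450/6000 = 0.075, SE = √(0.075 × 0.925 × 0.0012) = 0.00912, z = 0.030/0.00912 = 3.29, p = 0.001, ratio 0.10/0.07 = 1.43. Excluded: 350/4850 = 0.0722, ratio 1.39, z = 3.01, p = 0.0026.
- Break-even, where the expected result just reaches significance: about 1.9% lost (counted alive) to 2.1% lost (excluded). This lies inside the permitted range.

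**Chance of a significant result with no true effect** (simulation, pooled z test; each range runs from lost men excluded to lost men counted alive)

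| Controls lost | Share of the lost who are dead | False-significance rate |
|---|---|---|
| 1% | all | 16–18% |
| 2% | all | 47–55% |
| 3% | all | 82–88% |
| 3% | half | 25–34% |
| 3% | 30% | 10–15% |
| 3% | 10% (same as the cohort) | 5–6% |

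**Sensitivity, 3% lost and all dead**
- Exposed group also loses 3% at random: z = 2.97, p = 0.003.
- 1200 exposed men, 1:5: z = 3.29 to 3.60.
- One control per man, 1000 each: p = 0.016 to 0.028.
- Mortality 0.05: p < 0.0001. Mortality 0.15: p = 0.009 to 0.024. Mortality 0.20: p = 0.023 to 0.063.
- At 3% lost and 10% mortality, about 65 to 75% of the lost must be dead before the expected result is significant.

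These are unmatched tests. The matched 1:5 test should differ little unless within-set correlation is strong.

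**The case against.** The strongest reply is that the sections are compatible. V.B(1) and VIII.B state aims, V.B(1) covers only the exposed group, and VI.C itself prefers 1%. A reader might infer that the protocol sets two conflicting limits. The wording does not support that; an aim with an outer tolerance is coherent. What stands is that the tolerance is three times the aim offered as the remedy for this bias, and its consequence is not shown.

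A reader might also infer that the protocol predicts a false excess. Section VIII.B is conditional throughout: it says what may and could happen. The large figures need every lost control to be dead, which is 30% of control deaths missed, with no matching loss among RANCH HAND. The protocol plans tracing through Social Security, tax and VA records, VA death-benefit claims and death certificates. Equal loss of deaths in both groups would largely cancel. The 10% mortality is only an illustration; at 20% with lost men excluded the expected result just misses significance (p = 0.063).

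Finally, section VIII.D(3) promises that biases will be modelled before the final analysis of any phase and that conclusions will be tied to a bias estimate. This is relevant, although it sits under response bias. It is a general promise and fixes no bound for untraced men, so it does not make 3% a justified figure. Which bounding runs to perform could be left to an analysis plan, but the 3% tolerance is fixed in this document.

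**Conclusion.** The concern holds as a faulty tolerance in section VI.C. At the protocol's own illustrative rate and allocation, 1% and 3% have different consequences. The worst case at 1% gives an expected non-significant result (z = 1.00). At 3% it gives a strongly significant one (z = 3.01 to 3.29) with no true effect, and the crossover is near 2%.

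This rests on 10% mortality, 1000 against 5000 men, a two-sided 0.05 unmatched test, full tracing of RANCH HAND, and all lost controls being dead. Under milder assumptions the inflation is smaller, and it disappears or nearly so if the lost men die at the cohort's own rate. It would be wrong to conclude that 3% loss will produce a false excess, or that 1% removes the risk: the worst case at 1% still rejects 16 to 18% of the time. The point is worth correcting because the change is cheap and the direction of bias is one the protocol itself anticipates.

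**What to change.** In section VI.C, replace the range with one ceiling of 1% in each group, in line with V.B(1) and VIII.B. Extend the worked example to say that 3% unaccounted could alter a 0.10 control rate by as much as 30%.

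For all-cause mortality, report two bounds as a sensitivity analysis: unaccounted controls counted as dead with unaccounted RANCH HAND men counted as alive, and the reverse. State in the conclusion whether any observed excess could be explained by untraced controls.

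Surviving the bound should not be a condition for claiming an excess, and the bound should not be applied to cause-specific comparisons. Counting 1% of 5000 controls as dead adds 50 deaths to every cause. With 1% lost at random in both groups, simulation shows such a rule cutting power from 78% to about 43% for an all-cause ratio of 1.3 at 10% mortality. For a cause with 0.5% mortality and a true ratio of 3, it falls from 88% to 2%.

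The cost is a change of wording, two extra runs of the all-cause analysis, and a more cautious statement when tracing is incomplete. The 1% tracing effort is already the stated aim.

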KNOWN FACTORS	STUDY GROUP		POSSIBLE CONTROL GROUPS	
	RANCH HAND C-123	Non-RANCH HAND C-123	C-7	C-130
POPULATION SIZE	1200	3000	1200	25,000
OFFICER/ENLISTED RATIO	1:2	1:2	1:2	1:2
AIRCRAFT FUEL (AV-GAS)	YES (+JP-4)*	YES (+JP-4)*	YES	NO (JP-4 only)
OCCUPATIONAL HERBICIDE EXPOSURE	YES	YES/NO**	NO	NO
ESTIMATED FACTORS				
OCCUPATIONAL INSECTICIDE EXPOSURE	2+	1+ to 4+	0	0
COMBAT HAZARD	4+	3+	3+	2+
RVN-IN COUNTRY ASSIGNMENT	4+	4+	4+	2+

*In 1968, aircraft were modified with a JP-4 booster.

**Contaminated aircraft reconfigured for transport may have resulted in exposure to non-RANCH HAND personnel.

variables is as follows: (1) many clinical symptoms and signs allegedly attributed to herbicide exposure (see literature review) can also be attributed to an aging effect, or to collateral diseases more commonly associated with advancing age, (2) AFSC controls specifically for officer-enlisted status (as well as crewmember or noncrewmember status), a variable strongly linked to educational background, current socio-economic status, and moderately linked to age (5 year median difference) and socio-economic background, (3) total length of tour in RVN (measured in six month intervals, or actual flying hours, if feasible) will control for the generalized probability of combat morbidity, mortality, and for combat induced neuro-psychiatric disorders; additionally, length of tour may reflect effects related to intensity of alcohol consumption, drug consumption (chemoprophylactic or illicit), and degree of tropical disease acquisition and (4) race controls for differences in chronic disease development, socio-economic background, etc. (note: there is possible racial discordance for VA claimants).

(5) Study Group Selection Procedures

(a) Mortality Analysis

For the mortality analysis, ten controls will be selected for each exposed subject, regardless of current vital status (Figure 1). The control individuals will be randomly assigned to one of 10 cohorts, C₁ through C₁₀. All of the exposed individuals and a 50% random sample of each set of controls will be included in the mortality analysis. The current vital status of each exposed-control set will be determined, and their mortality experience will be followed throughout the duration of this study. In addition to providing a 1:5 mortality analysis, this technique will characterize the mortality experience of each control cohort.

[figure not shown]

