Since the death rates r_{1j} and r_{2j} are Poisson variables, they can be contrasted directly. If the relationship of r_{1j} to r_{2j} is found to be consistent between age strata (within statistical variability), a summary mortality index may be calculated. One summary index that will be calculated is Standardized Mortality Ratio (SMR) which is (Armitage, 1971):

$$SMR = M \times 100$$

$$M = \frac{\sum_{j=1}^k m_{1j}}{\sum_{j=1}^k P_{1j} r_{2j}}$$

"Classical" standardized mortality ratios using national mortality data as the reference will not be calculated for RANCH HAND II due to the effects of the healthy worker phenomenon. The term $\sum m_{1j}$ is the total number of deaths observed in the RANCH HAND group while $\sum p_{1j} r_{2j}$ is the number of deaths that would be expected were the age-specific RANCH HAND death rates the same as the age-specific control death rates. Thus the concern is for an SMR greater than 100%. If a crude death rate for controls, d_c , is calculated as

$$d_c = \frac{\sum_{j=1}^k p_{2j} r_{2j}}{\sum_{j=1}^k p_{2j}}$$

then the standardized crude rate for the RANCH HAND group d_{RH} is

$$d_{RH} = M d_c.$$

An approximate statistical test would regard r_{RH} as a Poisson random variable with mean d_c .

An alternative approach to the provision of a proportionate mortality ratio is that of Breslow and Day (1975). In this treatment, a multiplicative model is employed, for example:

$$\lambda_{ijk} = \theta_i \phi_j \psi_k$$

where λ_{ijk} is the mortality rate, θ_i is the contribution due to population differences (RANCH HAND versus Control), ϕ_j is the contribution due to age group, and ψ_k is the contribution due to tour length, etc. The statistical approach here is via maximum likelihood.

Logistic models (Walker and Duncan, 1967) have been extensively studied at USAFSAM for application in cardiovascular disease. These models, in the herbicide context would have the form

$$P = [1 + \exp(\alpha + \beta_1 A + \beta_2 T + \beta_3 R + \beta_4 E + \beta_5 AE + \dots)]^{-1}$$

where

P = probability of death
A = age in years
T = Vietnam tour length
R = indicator variable for race
E = exposure variable

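### The approximate SMR test treats the control death rate as known, so a nominal 5% test runs at about 7.4% in its normal form with five controls per man

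*Protocol*

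**What the plan says.** The passages are all in the protocol, mainly Section VI.C (Analysis of Mortality Data).

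- **Reference rates.** The SMR divides observed RANCH HAND deaths by the number expected "were the age-specific RANCH HAND death rates the same as the age-specific control death rates". An external reference is excluded because of the healthy worker effect: "standardized mortality ratios using national mortality data as the reference will not be calculated for RANCH HAND II".
- **The test.** The RANCH HAND rate `r_RH` is regarded "as a Poisson random variable with mean" `d_c`, the crude control rate. No variance is given for `d_c` or for the expected deaths. The symbol `r_RH` is not defined; the quantity just derived is `d_RH` = M × `d_c`.
- **Status of the control rates.** Earlier in the section both groups' rates are called random: "Since the death rates r_{1j} and r_{2j} are Poisson variables, they can be contrasted directly".
- **Number of controls.** Section V.B(5)(a) takes half of each set of ten: "In addition to providing a 1:5 mortality analysis, this technique will characterize the mortality experience of each control cohort". Section VI.C repeats this for the first analysis, "using available mortality data on the basic cohorts C' and R' (1:5 ratio". The later analysis enlarges the control group, "using mortality data on R' and all controls used in the study (both C' and replacements".
- **Other mortality analyses.** Section VI.C also lists a multiplicative model fitted by maximum likelihood, logistic models, and extensions of McNemar's test to R controls per exposed man. Section VI.E adds survival methods.

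**The concern.** A one-sample Poisson test is sound when the reference rate is effectively known, as a national rate would be. The protocol drops the national reference, for a good reason, but keeps the one-sample test. The replacement reference comes from a control group only about five times the size of the exposed cohort, and by the section's own account those rates vary at random. The test therefore counts the chance variation in RANCH HAND deaths and leaves out that in control deaths.

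The error makes p-values too small. Section VI.C is concerned with an SMR above 100, and false signals of excess mortality would be among the extra rejections.

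A smaller point is that the sentence applies the Poisson law to a rate. Deaths are Poisson; a rate is a Poisson count divided by person-years, so its variance does not equal its mean. Taken literally, the result would change with the unit in which the rate is expressed.

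**Working it through.** The protocol states no level, power or size for this test, so there is no figure of its own to reproduce.

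**Inputs**
- Controls per exposed man: k = 5 in the first analysis (Sections V.B(5)(a) and VI.C); at most k = 10 in the later one, since each set holds ten.
- Expected deaths E: 5 to 100. The upper value matches the illustrative control mortality of 0.10 in Section VI.C applied to the roughly 1000 men of Section VI.B.
- Nominal level: 0.05, borrowed from the power tables in Section VI.F. Both this level and two-sidedness are assumptions.

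**Variance**

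Let D be the RANCH HAND deaths and C the control deaths. With no effect, D ~ Poisson(E) and C ~ Poisson(kE), and expected deaths are estimated by C/k. Matching on age keeps person-years at about 1:k in every age stratum, so the same form holds after stratification.

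- Variance used by the test: E.
- Correct variance: Var(D − C/k) = E + E/k = E(1 + 1/k), which is 1.2E at k = 5.
- Ratio of standard errors, assumed to correct: 1/√1.2 = 0.913, an understatement of 8.7%. (Put the other way, the correct standard error is 9.5% larger.)

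**Level in the normal form**

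- k = 5: 2[1 − Φ(1.96/√1.2)] = 2[1 − Φ(1.789)] = 0.0736.
- k = 10: 2[1 − Φ(1.96/√1.1)] = 2[1 − Φ(1.869)] = 0.0617.
- One-sided 5% at k = 5: 1 − Φ(1.645/√1.2) = 0.0666.

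**Enumeration over D and C, nominal 5%, k = 5**

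| Expected deaths | Normal, two-sided | Exact tails, two-sided | Normal, one-sided | Exact tails, one-sided |
|---|---|---|---|---|
| 5 | 7.2% | 4.8% | 8.5% | 5.3% |
| 10 | 7.3% | 5.3% | 8.3% | 5.8% |
| 20 | 7.3% | 5.9% | 7.7% | 5.8% |
| 50 | 7.4% | 6.4% | 7.3% | 6.1% |
| 100 | 7.4% | 6.7% | 7.1% | 6.2% |

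A simulation with five age strata gave 7.3% to 7.4% two-sided in the normal form at 20, 50 and 100 expected deaths.

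With exact tails and few deaths, discreteness hides the error. If the mean really were known, the exact two-sided test would run at 2.0% for E = 5 and 2.5% for E = 10; ignoring control error raises these to 4.8% and 5.3%.

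**After correction, k = 5**

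Conditional on D + C, D is Binomial(D + C, 1/6). The two-sided level is 5.0% in the normal form at 20, 50 and 100 expected deaths, and 3.8%, 4.2% and 4.4% in the exact conditional form.

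**The case against.** The strongest reply is that the sentence is tentative and has sound company. It is worded conditionally, it calls the test approximate, and it fixes no level or decision rule. The SMR is one summary index among several and depends on consistent rate ratios across age strata. The multiplicative, logistic and R-to-1 matched analyses use both groups' data, as do the survival methods of Section VI.E. Section VIII.A also foresees falling back on multiplicative or logistic models if the classical comparison cannot be validated.

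Most of this stands, and it limits the harm. It does not correct the sentence. Calling the test approximate does not cover an omission that persists as deaths accumulate: the normal-form level is 7.4% at both 50 and 100 expected deaths.

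Four stronger readings are tempting, and the documents do not support them.

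- *SMR confidence intervals are too narrow.* Section VI.C specifies none.
- *Because a rate is not Poisson, the test has no reference distribution.* With person-years taken as fixed, a rate is a scaled Poisson count, and the section uses that shorthand throughout. The wording needs repair, but this adds nothing to the 7.4%.
- *All cause-specific p-values are too small.* With few deaths and exact tails, the two-sided level is near or below 5%.
- *The test carries over to questionnaire and examination findings, where there is one control per man and the level would be 16.6%.* Section VI.D does refer back to the mortality tools, but it assigns the significance of relative risks to logistic models and McNemar's test.

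**Conclusion.** The test is wrong as stated, and the effect is modest. At five controls per man its two-sided level is about 7.4% in the normal form. With exact Poisson tails it is 5.9% to 6.7% at 20 to 100 expected deaths, with little or no excess over 5% at 10 or fewer. If all ten controls in every set entered the later analysis, the normal-form level would fall to about 6.2%.

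These figures rest on four assumptions: a nominal two-sided 5%, which the protocol does not state for this test; a test on death counts, not literally on rates; person-years as the denominator, as in Table 7; and no within-set correlation beyond age. Positive correlation from matching on specialty code, tour length and race would reduce the excess.

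A reader might infer that the mortality study as a whole is biased towards finding an effect. The documents do not support that, since the other listed mortality analyses do not use this test. The defect lies in one sentence.

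**What to change.** Replace the sentence that states the test, in one of two ways.

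1. Test the number of RANCH HAND deaths, conditional on total deaths in each age stratum: m_1j ~ Binomial(m_1j + m_2j, P_1j/(P_1j + P_2j)), combined over strata, for example by a person-time Mantel-Haenszel statistic.
2. Take the SMR test from the multiplicative model already in Section VI.C, with control deaths modelled as random.

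In either case refer to deaths and not to the rate as the Poisson variable, and replace the undefined `r_RH` with a defined symbol. State the level and sidedness in the same place.

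No further data are needed. The cost is slightly larger p-values. At 100 expected deaths in the normal form, the two-sided 5% threshold for an excess moves from 1.96 × √100 = 19.6 deaths to 1.96 × √120 = 21.5, that is, from an SMR of about 119.6 to about 121.5.
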